Evaluation of the impact of the HLNatural, Inc. Upset Stomach Relief product on the reduction of symptoms in adults who suffer from mild to moderate indigestion and heartburn

NCT04153552

Day Month Year July, 17th 2019

Evaluation of the impact of the HLNatural, Inc. Upset Stomach Relief product on the reduction of symptoms in adults who suffer from mild to moderate indigestion and heartburn

Sponsored by: HLNatural, Inc.

Principal Investigator:[name]

Version Number
Version 1.1

Day Month Year July, 17th 2019

Statement of Compliance

The study will be carried out in accordance with Good Clinical Practice (GCP) as required by the following:

- U.S. Code of Federal Regulations applicable to clinical studies (45 CFR 46)
- ICH GCP E6
- Completion of Human Subjects Protection Training
- NIH Clinical Terms of Award

Refer to:

https://www.hhs.gov/ohrp/regulations-and-policy/guidance/faq/45-cfr-46/index.html https://www.ich.org/fileadmin/Public Web Site/ICH Products/Guidelines/Efficacy/E6/E6 R2_ Step 4 2016 1109.pdf

http://grants.nih.gov/grants/quide/notice-files/NOT-OD-01-061.html https://www.fda.gov/drugs/quidance-compliance-regulatory-information/quidances-drugs

SIGNATURE PAGE

The signature below constitutes the approval of this protocol and the attachments and provides the necessary assurances that this trial will be conducted according to all stipulations of the protocol, including all statements regarding confidentiality, and according to local legal and regulatory requirements and applicable US federal regulations and ICH guidelines.

Principal	Investigato	or:	
Signed:			Date:
	Name		
Project N	/lanager:		
Signed:	Name		Date:
	nume		
Sponsor:			
Signed:			Date:
Signeu.	Name		Date.
Statistici	an		
Statistici	dII		
Signed:	Name		Date:
	Nume		
Title:		Evaluation of the impact of the HLNatural, In product on the reduction of symptoms in ad	•
		moderate indigestion and heartburn	
Populatio	n:	The study will consist of at least 200 particip	ants who self-identify as
		satisfying the inclusion criteria. The geograph	ny of participant enrollment
		will be spread across the United States.	

Number of Sites: This is a single (virtual) site study.

Study Type Single site, prospective, one arm observational study of Minimal Risk.

Study Duration: The duration of the study is expected to be 6 months depending on the

speed of enrollment.

Participant Duration: The duration of participation for each participant is expected to be 60

days.

Objectives: The purpose of this study is to demonstrate whether this plant-based

remedy will reduce the severity of symptoms of occasional indigestion and heartburn. This trial will gather data on performance of the test product. These data will be used to describe the performance currently,

and potentially to design a two-arm trial in the future

Primary Endpoints:

• The primary endpoint is reduction in indigestion severity and reduction in heartburn severity. There is no control group for the primary analysis.

Secondary Endpoints:

- The time to other intervention will be analyzed.
- A longitudinal analysis will be performed for participants who report on more than one incident of heartburn or indigestion.
- Adverse events will be summarized.
- An additional data presentation will consist of results from both Treatment and Control in similar studies appearing in the literature. There will be no formal statistical comparison of results from this study and historical studies.
- The Net Promoter Score will be summarized and compared against outcomes.
- Comparison against normal behavior will use the paired sample t-test

Table OF Contents

1.	KEY	ROLES	
2.	Back	kground Information and Scientific Rationale	
		Background Information	
2	2.2.	Scientific Rationale	10
	2.2.1.	. Potential Risk	10
	222	Known Potential Benefits	11

3. Study Objectives	12

2.1. Background Information

The primary hypothesis of the present study is that supplementation with the Upset Stomach Relief test product will reduce the severity of the symptoms of occasional indigestion and heartburn.

Dyspepsia, also known as indigestion, is a common symptom with an extensive differential diagnosis and a heterogeneous pathophysiology. It occurs in approximately 25 percent of the population each year, but most affected people do not seek medical care. Approximately 25 percent of patients with dyspepsia have an underlying organic cause. However, up to 75 percent of patients have functional (idiopathic or non-ulcer) dyspepsia with no underlying cause on diagnostic evaluation. Patients with functional dyspepsia usually describe postprandial fullness, early satiety, and/or epigastric pain/burning. Symptoms may be severe enough to limit usual activities. Some patients may have nausea, vomiting, or heartburn; however, these symptoms are usually infrequent. [28] The most common approach to treat occasional indigestion and heartburn is to use antacids to neutralize what is often believed to be an overproduction of stomach acid. This acidblocking approach can perpetuate the problem when used over a long period of time. Acid blocking also has the drawback of causing deficiencies in certain vitamins and minerals over time, such as calcium. By interfering with the digestive process, an overgrowth of bacteria and imbalances in gut health can also worsen health states. The Upset Stomach Relief test product is an herbal solution with ingredients that may ease occasional indigestion and heartburn, while helping to strengthen the digestive tract over time. [4]

There are several causes of indigestion. Acid accumulation and improper gastrointestinal emptying can both prompt dyspepsia. Additionally, stomach or intestinal ulcers formed by bacteria named *Helicobacter pylori* can result in infection that ultimately will cause indigestion. Other potential causes can be from the intake of over-the-counter medications, like ibuprofen, overeating, fatty, greasy, or spicy food, alcohol, and caffeine. [5]

While dietary and lifestyle changes can ease the symptoms of indigestion and heartburn, HLNatural, Inc. created the test product to reduce occasional indigestion and heartburn. The test product is a plant-based remedy formulated with ingredients that have demonstrated

efficacy reducing symptoms associated with occasional indigestion and heartburn. The product combines ingredients into an easy to consume capsule designed to be consumed at the onset of symptoms or before each meal, up to three times per day. The test product is 1) DGL Extract, 2) Artichoke Leaf Extract, 3) Ginger Root Extract (6% gingerols), 4) Chamomile (1% Apigenin), 5) Marshmallow Root Extract, 6) Capsule (Hydroxypropyl Methyl Cellulose, Purified Water, Carrageenan, Potassium Chloride), , 7) Rice Hull Concentrate. Below, the 7 ingredients of the test product are listed. All ingredients are Generally Recognized as Safe (GRAS) by the FDA.

Upset Stomach Relief

Active Ingredients: Licorice Extract, Artichoke Leaf Extract, Chamomile, Marshmallow Root, Ginger.

Inactive Ingredients: Capsule (Hydroxypropyl Methyl Cellulose, Purified Water, Carrageenan, Potassium Chloride), Rice Hull Concentrate.

The ingredients in the test product have been included because they have demonstrated benefit for digestive health. The justifications for their inclusion are briefly described here:

Licorice has a long history of traditional use in promoting digestive health. DGL is a type of extract of licorice in which the glycyrrhizin has been removed, which helps prevent side effects that can occur in some people from regular Licorice use. Scientific investigation into the mechanism of activity of DGL for providing digestive support shows that it helps in maintaining digestive comfort by maintaining the integrity of the protective mucosal lining in the stomach and intestine. It is also an anti-spasmolytic, which helps to relax the intestinal wall and aid in digestive comfort. [10, 16, 17, 18]

Artichoke Leaf Extract helps stimulate and aid the digestive process. Artichoke Leaf extract is a traditional herbal digestive bitter known to stimulate the digestive process. Artichoke Leaf extract has been shown in studies to relieve occasional heartburn. [9]

Marshmallow Root has a long history of traditional use for soothing mucosal membranes. The mucilage-rich roots of Marshmallow are thought to be responsible for many of the pharmacological activities of Marshmallow. Preclinical research shows that the mucilaginous nature can help form a protective coating on the mucosal lining, which acts as a shield from irritants and exerting spasmolytic and antisecretory properties. [11, 19, 20, 21, 22]

Ginger is a spice that has long history of traditional use for digestive discomfort. Clinical research shows that Ginger supports health through its benefits to the immune, respiratory

systems, aiding digestion, and promoting normal cytokine balance. Ginger works on the gutbrain axis by supporting neurotransmission which supports gastric emptying, upper GI digestive comfort and intestinal motility. It exerts a gastroprotective effect and relief of occasional heartburn. [7, 8, 23, 24]

Chamomile is one of the most world-renowned herbs for promoting healthy digestion. It contains a phytochemical called apigenin which has a number of health-promoting benefits, including promoting healthy cytokine balance. Chamomile is also antispasmodic, affecting the muscles of the intestine and promoting digestive comfort. Additionally, stress and mood have been proven to affect indigestion and in clinical studies, Chamomile has shown support for relaxation and healthy mood. [3, 6, 25, 26, 27]

2.2. Scientific Rationale

The test product's formulation is based on the most promising clinical research on natural ingredients that safely impact digestive health and relieve symptoms of occasional indigestion and heartburn. While the evidence to support the use of these individual active ingredients is growing, well-designed human clinical trials showing benefit are necessary to demonstrate efficacy of the test product's unique formulation.

The present study will include a minimum of 200 participants who suffer from the symptoms of mild to moderate indigestion and/or heartburn and is designed to observe the level of symptom reduction in this population after consuming the test product.

2.2.1. Potential Risk

Minimal risk is foreseen for participants through their participation in the study. All the ingredients composing the test product are Generally Recognized as Safe (GRAS) by the FDA for daily consumption at their present concentrations.

The ingredients in the test product have been shown to have some theoretical drug interactions which have been listed in the appendix. (*Appendix A*)

Potential side-effects have been observed in high doses which are significantly greater than the dose of the capsules as recommended in the instructions for use:

- Headache
- Amenorrhea
- Upset Stomach
- Diarrhea
- Hives
- Difficulty breathing
- Facial swelling

- Drowsiness
- Tiredness
- Vomiting

This study is determined by Sponsor and Principal Investigator to be a Minimal Risk Study.

Minimal risk is defined by 45 U.S. Code of Federal Regulations (CFR) 46.102 (i) as follows:

"Minimal risk means that the probability and magnitude of harm or discomfort anticipated in the research are not greater in and of themselves than those ordinarily encountered in daily life or during the performance of routine physical or psychological examinations or tests."

Refer to: http://www.hhs.gov/ohrp/humansubjects/quidance/45cfr46.htm#46.102

2.2.2. Known Potential Benefits

Over-the-counter and prescription remedies for occasional indigestion and heartburn have known undesirable side effects. Additionally, these products often contain additives, dyes, fillers and other unnatural or synthetic ingredients that consumers are looking to avoid. As such, these consumers are seeking natural, plant-based alternatives for symptom relief. Research participants may benefit from the intervention by eliminating such unwanted side effects when treating their symptoms of occasional indigestion and heartburn while achieving symptom relief. If the intervention is shown to be efficacious, this would provide a viable solution for those people who want to decrease their use of drugs that contain undesired ingredients. Other benefits include detailed surveillance of symptoms and documentation of activities, routine medications and supplements that may provide participant and their regular physician or other healthcare provider with useful information for diagnosis and treatment of symptoms should they occur.

2.2.3. Minimization of Risks

Research participants will be carefully screened to meet enrollment criteria. Participants meeting exclusion criteria will not be enrolled. The study participant informed consent will be presented with clear description of the study requirements and opportunity to have questions answered before enrollment. Once an event occurs, review of symptoms will be ascertained at onset, 15, 30, and 60 minutes. Reporting of adverse events will be reviewed routinely and in accordance with regulatory guidelines (21CFR, GCP) by the Principal Investigator. Participants with occurrence of worsening symptoms or adverse

events will be advised to stop taking the test product, may seek medical attention, and exit the study.

3. Study Objectives

The purpose of the present study is to evaluate 1) the impact of the test product on symptoms of occasional indigestion and heartburn in 200 adult participants who suffer from occasional indigestion and heartburn and 2) the subjective experience of these participants related to general health, indigestion and heartburn symptoms, and personal experience with the test product.

This will be evaluated based on the primary and secondary endpoints. These endpoints, the analysis populations, and their respective measures are described below. Further details on the methods for measuring the outcomes can be found in the Study Outcome Measures and Analysis Plan sections.

Primary Endpoint:

The primary endpoint has two components, reduction in indigestion severity and reduction in heartburn severity. Participants will be asked to rate each symptom (bloating, early fullness during a meal, pain or discomfort in the upper abdomen, burning in the upper abdomen, pain/burning in the center of your chest, nausea, vomiting, and burping) on a 4-point scale at 4 time points: prior to taking the test product, 15, 30, and 60 minutes after taking the test product. The improvement in symptoms from baseline will be evaluated on a pairwise basis separately for each component and each time point. P-values will be computed for the improvement. Given that indigestion can impact an individual's quality of life, the primary endpoint was chosen to see the test product's effects on symptoms. [1, 9, 12]

Secondary Endpoint:

Secondary endpoints will be analyzed to evaluate safety and patient satisfaction with relief of symptoms. These include:

- The time to other intervention will be analyzed.
- A longitudinal analysis will be performed for participants who report on more than one incident of heartburn or indigestion.
- Adverse events will be summarized.
- An additional data presentation will consist of results from both Treatment and Control
 in similar studies appearing in the literature. There will be no formal statistical
 comparison of results from this study and historical studies.
- The Net Promoter Score will be summarized and compared against outcomes.
- Comparison against normal behavior will use the paired sample t-test.

4. Study Design

The present study will be a single site, prospective, one arm observational study of minimal risk consisting of at least 200 participants who suffer from symptoms of occasional indigestion and heartburn. The participants must meet additional inclusion/exclusion criteria (see Inclusion/Exclusion Criteria). Participants will begin taking the capsules at the onset of indigestion and heartburn symptoms. Onset is defined as the point in time the participant takes the test product for relief of symptoms. When the participant decides to take the test product, they will report and rate their symptoms on a 4-point Likert scale in the symptom diary prior to taking the test product. After consuming the test product, the participant will complete a 4-point Likert scale for each symptom at 15 minutes, 30 minutes, and 1 hour after taking the test product. If needed the participant will be allowed to take an alternative medication an hour after taking the test product. If medication is taken, the participant will record this in their symptom diary.

Study enrollment and management will be decentralized, where participants do not visit an investigator or a clinic for clinical assessment. The participants will participate in the study at home. All data collected from during this study will be reported by the participant via eCRFs, eDiary, and other electronic data entries. If a visit is required, it will be conducted via remote contact by telephone.

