- After completing the surveys, the participant will take the test product. The participant will take
 2 capsules per indigestion and heartburn episode. With a max of 6 capsules per day. (If
 participant takes 6 capsules in 1 day this will be defined as 3 indigestion and heartburn episodes
 and the participant will be exited from the study).
- After taking the test product, the participant will complete a 4-point Likert scale assessment for each symptom at 15 minutes, 30 minutes, and 1 hour after taking the test product.
- When the participants symptoms have resolved , the participant will complete the symptom diary.
- If the participant takes any other medication outside of the test product, the participant will record this on the symptom diary.
 - The participant is allowed to take alternative medications or supplements AFTER 1 hour from taking the test product.
- After taking the test product, the participant will be instructed to fill out an Adverse Event form for any side-effects experienced.
- After the first episode of indigestion and heartburn, the participant will be asked to complete the same process for another 2 episodes within the 60-day study time frame; however, these are not required.
- If the participant completes the required assessments for a total of 3 episodes of indigestion and heartburn, they will be prompted, by email, to exit the study.
- If the participant only completes the required assessments for the required 1 episode of indigestion and heartburn, the participant will be prompted, by email, to complete the study exit form and will be exited from the study on day 60 (60 days from the day of receipt of the test product).
- Neither the sponsor nor Hawthorne Effect Inc. will not collect any unused test product.
- Upon receipt of study exit survey and review of completed study forms, participant will receive an Amazon gift card of \$25 via email.

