6.4. Adverse Event and Safety Monitoring

Adverse Events (AEs) are defined as any untoward medical occurrences described by the study participant. All AEs will be self-reported and documented on the platform. The AEs will be reviewed by the study team including the remote trial coordinator and study principal investigator and reported according to the IRB requirements. Participants who experience adverse events will be advised to seek medical attention.

In the event that a participant experiences an adverse event, the clinical study manager or clinical ops coordinator will notify both the PI and Sponsor. The Sponsor will take appropriate action according to their standard operating procedures for any adverse events that warrant action by the sponsor.

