7.1. Study Outcomes Measures

Analysis populations:

The *intent to treat* (ITT) population consists of all participants who are consented, report the onset of indigestion and heartburn, and have taken the study medication at least once. The primary analysis will be in the ITT population.

Primary Endpoint:

The primary endpoint has two components, reduction in indigestion severity and reduction in heartburn severity. Participants will be asked to rate each symptom (bloating, early fullness during a meal, pain or discomfort in the upper abdomen, burning in the upper abdomen, pain/burning in the center of your chest, nausea, vomiting, burping) on a 4-point Likert scale at 4 time points: prior to taking the test product, 15, 30, and 60 minutes after taking the test product. The improvement in symptoms from baseline will be evaluated on a pairwise basis separately for each component and each time point. P-values will be computed for the improvement.

There is no control group for the primary analysis.

Secondary Endpoints:

Secondary endpoints will be gathered on the subjective experience of these participants related to general health, personal experience with the test product. The secondary endpoints will be self-reported by the participant on their online portal. There will be a questionnaire related to general health and the subjective experience of the participant administered at baseline and at study exit.

The purpose of the secondary analyses is to investigate the association between various baseline and other measurements and outcomes. These secondary analyses are considered hypothesis generating, and the descriptions are somewhat informal. The trial data may suggest secondary analyses not described here.

Secondary endpoints:

- The time to other intervention will be analyzed.
- A longitudinal analysis will be performed for participants who report on more than one incident of heartburn or indigestion.
- Adverse events will be summarized.
- An additional data presentation will consist of results from both Treatment and Control
 in similar studies appearing in the literature. There will be no formal statistical
 comparison of results from this study and historical studies.
- The Net Promoter Score will be summarized and compared against outcomes.
- Comparison against normal behavior will use the paired sample t-test.

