13.1.7. Appendix G Adverse Event Form

Upset Stomach AE document

- 1. Did you experience any side effects after taking the test product? Y/N
 - a. If so, did you experience any of the following
 - o itching, rash, hives, throat/lip/tongue swelling, wheezing
 - low blood pressure, fainting, chest pain, shortness of breath, palpitations, irregular heart beat
 - o severe, persistent nausea, vomiting, diarrhea, or abdominal pain
 - o difficulty urinating, decreased urination
 - o fatigue, appetite loss, yellowing skin/eyes, itching, dark urine
 - severe joint/muscle pain
 - o slurred speech, one-sided weakness of face, arm, leg, vision
 - o abnormal bleeding from nose or gums
 - o blood in urine, stool, vomit,
 - o marked mood, cognitive, or behavioral changes, thoughts of suicide
 - o Other:
- 2. Please give a description of the event
- 3. How soon after taking the test product did you experience the side effect?
- 4. What did you do to alleviate the side effect?
- 5. Did you have to go to the hospital or see a doctor for this side effect?
 - a. Please describe any diagnosis or treatment that they provided.
 - b. If you were seen in the hospital, please upload any discharge paperwork or other documents from the hospital.

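### The protocol gives different actions after an adverse event in sections 2.2.3, 6.1 and 6.4, and post-dose worsening enters the safety summary only if the participant calls it a side effect

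*Combined protocol and SAP*

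**What the plan says.** Section 2.2.3 sets two triggers. The sentence opens "Participants with occurrence of worsening symptoms or adverse" and continues "events will be advised to stop taking the test product, may seek medical attention, and exit the study". The same section offers symptom review at onset and at 15, 30 and 60 minutes as a means of limiting risk.

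Section 6.4, the safety monitoring section, defines the term broadly: "Adverse Events (AEs) are defined as any untoward medical occurrences described by the study participant". Capture is by the participant: "All AEs will be self-reported and documented on the platform". The coordinator and principal investigator review these reports, and the principal investigator and sponsor are notified. On action it says: "Participants who experience adverse events will be advised to seek medical attention".

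After a first episode, section 6.1 says "the participant will be asked to complete the same process for another 2 episodes within the 60-day study time frame", and adds that the further episodes are optional. It ends participation after three episodes or at day 60, and section 4.3 does the same.

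The symptoms rated for efficacy in section 7.1 include "pain/burning in the center of your chest, nausea, vomiting, burping". Section 6.4.1 lists vomiting as an anticipated adverse event. The adverse event form in Appendix G lists "low blood pressure, fainting, chest pain, shortness of breath, palpitations, irregular heart beat". Section 11 states as a limitation that symptoms are not medically reviewed.

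**The concern.** Staff who receive an adverse event report cannot tell from the protocol what the participant is to be told, or whether that person stays in the study. The worsening trigger in section 2.2.3 is not defined on the 0 to 3 scale. No section names who would notice worsening, or when.

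The statistical consequence is in the safety summary. Some events that count as harm in section 6.4.1 and Appendix G are also efficacy items. If the participant regards such a change as part of the episode, it is recorded as an efficacy score and does not appear among the adverse events. The trial would then hold evidence of deterioration on treatment that none of its planned tables displays.

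**Working it through.** No sample size, power or event figure in the plan bears on this point, so the check is mainly a comparison of the text.

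**1. Actions after an event**

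| Section | Trigger | Stop product | Medical care | Exit |
|---|---|---|---|---|
| 2.2.3 | Adverse event or worsening | Advised | Optional | Yes |
| 6.4 | Adverse event only | Silent | Advised | Silent |
| 6.1 (and 4.3) | Neither | Silent | Silent | Three episodes or day 60 only |

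Sections 2.2.3 and 6.4 differ on the strength of the advice about care. Stopping, exit and the worsening trigger appear only in 2.2.3. Section 6.1, which participants and staff would follow, carries none of it.

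**2. Symptom review.** Section 2.2.3 counts it as a protection. Section 11 says there is no medical review of symptoms. Both can be true only if review in 2.2.3 means collecting ratings, and in that case nobody is assigned to act on them.

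**3. Overlap of harm and efficacy items.** Vomiting is on both lists (6.4.1 and 7.1). Chest pain on the Appendix G form overlaps the rated item on pain or burning in the centre of the chest. No rule says when a rated symptom becomes an adverse event.

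**4. Tracing a vomiting score that goes from 0 before dosing to 3 afterwards**
- The 15, 30 and 60 minute pages of Appendix E hold symptom ratings only.
- Section 6.2 marks an adverse event assessment at each of those times and at exit. The forms shown that ask about adverse events are the closing question of the diary and the Appendix G form, and both ask about side effects.
- The closing question comes in the part of the diary completed after symptoms resolve.
- Section 6.1 asks for an adverse event form for any side effect. Appendix G names vomiting only when severe and lasting, but has an open category.
- Review in section 6.4 starts from what has been self-reported as an adverse event.

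The score therefore reaches review if the participant attributes it to the product, and not otherwise. The definition in section 6.4 is wide enough to include it, but the forms ask a narrower question.

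**5. What the planned tables show.** Section 7.1 names 8 symptoms, each rated at 3 post-dose times: 8 x 3 = 24 post-dose ratings per episode, or 24 x 3 = 72 over three episodes. Section 7.3 plans mean changes with paired t-tests, and frequency counts for short scales.

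A constructed example on the 0 to 3 scale shows the gap. Four participants rate a symptom 3, 3, 3, 0 before dosing and 0, 0, 0, 3 after.
- Mean improvement: (3 + 3 + 3 - 3) / 4 = 1.5.
- Count at severe: 3 before, 1 after.

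Both summaries look favourable, yet the one severe score after dosing belongs to someone who had no symptom before. Marginal counts cannot distinguish that person from one whose severe symptom simply persisted.

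**The case against.** The strongest reply is that a safety route exists and is used often. The schedule has an adverse event assessment at every rating time, the diary asks about side effects and sends a yes to the form, the form lists chest pain and vomiting, and section 6.4 provides review and notification. This stands. A reader might infer that diary worsening reaches nobody, or can only ever be an efficacy score. The documents do not support that.

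Section 6.4 is also silent on stopping and exit; it does not countermand section 2.2.3. That is fair, but the wording on medical care still differs, and section 6.1 is silent on all of it.

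A reader might infer from section 6.1 that participants are pressed to dose again after an adverse event. The further episodes are expressly optional, so that does not hold.

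Nor can one infer that participants are never told what to do if they get worse. Consent pages were removed from the text available, and the product insert listed as Appendix H is not in it.

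The absence of medical review is a disclosed limitation of a self-report study judged to be of minimal risk. Disclosure does not settle its conflict with section 2.2.3.

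Finally, symptoms may rise after dosing because the episode is still developing; the Appendix D form allows a peak more than an hour after onset. This is a good reason not to treat every rise as harm, and it limits how the table proposed below can be read.

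**Conclusion.** The point holds in two parts.

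First, sections 2.2.3, 6.1, 6.4 and 11 do not give one account of what follows an adverse event or worsening, and must be reconciled. This rests on the text alone.

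Second, post-dose worsening in a rated symptom reaches safety review and the adverse event summary only through the participant's own judgement that it is a side effect. Neither the mean changes nor the frequency counts would show it person by person.

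The size cannot be given as a number of participants. The documents contain no rate of post-dose worsening and no rate of self-reporting, and the number missed could be zero if everyone who worsens files a form. A reader might also infer that the protection in section 2.2.3 does not work at all; the self-report route shows that to be too strong. The primary efficacy analysis is not invalidated. What suffers is the clarity of the safety instructions and the completeness of the safety summary.

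**What to change.** **Wording.** Reconcile sections 2.2.3, 6.1, 6.4 and 11 so that the same statement of what happens after an adverse event or worsening appears in each. Its content, including what counts as worsening, is for the sponsor and investigator. State whether symptom review in section 2.2.3 means that someone reads the ratings or only that they are collected.

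**Table.** In the safety summary, add for each rated symptom:
- the number of participants with a pre-dose and at least one post-dose rating;
- the number with any post-dose rating above their pre-dose rating;
- the number newly severe, meaning below 3 before dosing and 3 at any time after.

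Say how blanks are handled, since section 6.1 asks for ratings of the symptoms being experienced and a symptom absent before dosing may have been left blank. Describe the table as including natural fluctuation, because there is no control group. No automatic alert for every one-point rise is proposed: it would set a clinical threshold and would mostly raise review workload.

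**Cost.** A protocol wording change and one extra table from data already collected. The downside is that some of what the table shows will be the natural course of the episode, and it cannot be attributed to the product.
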